5. TREATMENT

5.1 Overview

The study will enroll patients with CLL and NHL in a dose escalation and subsequent expansion. First, patients with relapsed or refractory disease will be enrolled in a dose finding study that will assign doses for each patient using a modified continuous reassessment method using software developed by Piantadosi (Modified Continual Reassessment Method, version 4.0). Up to 10 patients with CLL and 10 patients with NHL will be treated at the estimated MTD as part of the expansion.

In August 2016 after 2 patients were treated at dose level 2 for 1 cycle, both reported significant fatigue and anorexia. While not technically DLT, these AEs were concerning to the investigators, and after discussion with the DSMC it was decided to return to dose level 1 for continued expansion. This was discussed with Karyopharm, who reported increased tolerability

and efficacy using once weekly dosing strategies in other studies.

Cohort 3, which will initiate after the dose escalation and expansion, will add selinexor administered weekly (days 1, 8, and 15 of each cycle) at 40 mg PO, to patients receiving ibrutinib as frontline therapy for at least 12 months. Selinexor plus ibrutinib will be administered for 14 cycles, with discontinuation of selinexor after 14 cycles. At the end of 14 cycles, patients who achieve a minimal residual disease (MRD) negative response may have both drugs discontinued at the discretion of the treating physician. Patients who are MRD positive at the end of 14 cycles will discontinue selinexor and are recommended to continue ibrutinib.

5.2 Agent Administration

Treatment will be administered on an outpatient basis. Reported adverse events and potential risks are described in Section 7. Appropriate dose modifications are described in Section 5. No investigational or commercial agents or therapies other than those described below may be administered with the intent to treat the patient's malignancy.

Regimen Description					
Agent	Precautions	Dose	Route	Schedule	Cycle Length
Ibrutinib	Take with 8 oz of water, 30 min before meal	Capsule or tablet*	Oral	Cycle 1 Days 8-28**, Cycles 2+ Days 1-28	28 days (4 weeks)
Selinexor	Take with at least 120 mL (4 ounces) of fluids (water, juice, etc.)	Tablet*	Oral	Days 1, 8, and 15 of each cycle *	
*Doses/schedule as appropriate for assigned dose level.					
**Patients continuing on ibrutinib should take ibrutinib days 1-28 of Cycle 1					

Dose Level	Selinexor Dose	Selinexor Schedule	Ibrutinib Dose	Ibrutinib Schedule
1*	40 mg	Weekly (oral)	420 mg	Daily (oral)
2	20 mg	Bi-weekly (oral)	420 mg	Daily (oral)

5.2.1 Study Drugs Description

5.2.1.1 Selinexor is an oral selective inhibitor of nuclear export.

Selinexor is manufactured by KABS Laboratories (Montreal, ON) for Karyopharm, Therapeutics (Newton, MA) using methods in accordance with Food and Drug Administration (FDA) guidelines for the manufacture and testing of antineoplastic agents for human use. The tablets are prepared from a common blend of excipients and all tablet excipients are GRAS (generally regarded as safe) listed and suitable for use in pharmaceuticals. Selinexor is an investigational agent supplied to investigators of this study by Karyopharm Therapeutics at no cost.

5.2.1.2 Ibrutinib is an oral inhibitor of Bruton's tyrosine kinase. The compound is manufactured by Pharmacyclics, Inc (Sunnyvale, CA) using methods in accordance with Food and Drug Administration (FDA) guidelines for the manufacture and testing of antineoplastic agents for human use.

5.2.2 Drug Products Composition and Preparation

5.2.2.1 Selinexor

Selinexor will be supplied in 20 mg tablets in wallet-sized blister packs (12 tablets per blister pack). Each wallet-size blister package of selinexor tablets will be labeled in accordance with current International Conference on Harmonization (ICH), Good Clinical Practice (GCP), and specific regulatory requirements, e.g., FDA, Health Canada, EMA, etc. Blister packages for take-home use may require additional in-pharmacy labeling with take-home and patient-specific instructions (such as exact dose) depending on country-specific regulations or laws.

5.2.2.2 Ibrutinib

Ibrutinib for oral administration is supplied as either capsules or tablets. The capsules are hard gelatin capsules containing micronized ibrutinib and the following excipients: microcrystalline cellulose; croscarmellose sodium; sodium lauryl sulfate; may contain magnesium stearate. Capsules are manufactured as 140mg in a size 0, gray, hard gelatin capsule. Capsules are packaged in high-density polyethylene (HDPE) bottles with an induction seal and a child resistant screw top cap. Each bottle contains 92 capsules. Ibrutinib capsules are to be dispensed in their original containers. The tablet formulation is manufactured as 140, 280, or 420 mg and is dispensed as a blister pack.

5.2.3 Selinexor Administration

Each dose will consist of selinexor tablet(s) for oral administration on a fixed dose basis. Dose levels for the study are 40 mg once weekly and 20 mg twice weekly. If needed, the level (-1) de-escalation dose level will be 20 mg weekly. Selinexor oral doses are given Days 1, 8, and 15 of each 28 day cycle.

Selinexor tablets are to be taken with at least 120 mL (4 ounces) of fluids (water, juice, etc.) at approximately the same time each day. Selinexor tablets should not be crushed because of increased risk of dermatologic toxicity if the powder comes in contact with skin.

5.2.4 Ibrutinib Administration

Ibrutinib should be taken with 8 ounces (approximately 240 mL) of water (avoid grapefruit or Seville orange juice due to CYP450 3A4 inhibition). Each dose of ibrutinib should be taken at least 30 minutes before meal, at approximately the same time each day. The capsules or tablets should be swallowed intact and subjects should not attempt to open capsules or dissolve them in water.

If a dose is missed, it can be taken up to 6 hours after the scheduled time with a return to the normal schedule the following day. If it has been greater than 6 hours, the dose should not be taken and the subject should take the next dose at the scheduled time the next day. The missed dose will not be made up and must be reported at the next scheduled visit.

Ibrutinib should be held for any procedure using the following guidelines:

- For any surgery or invasive procedure requiring sutures or staples for closure, ibrutinib should be held at least 7 days prior to the intervention and should be held at least 7 days after the procedure and restarted at the discretion of the investigator when the surgical site is reasonably healed without serosanguineous drainage or the need for drainage tubes.
- For minor procedures (i.e. such as a central line placement, needle biopsy, thoracentesis, or paracentesis) ibrutinib should be held for at least 3 days prior to the procedure and should not be restarted for at least 3 days after the procedure. For bone marrow biopsies that are performed while the subject is on ibrutinib, it is not necessary to hold ibrutinib for these procedures.
- For emergency procedures, ibrutinib should be held after the procedure until the surgical site is reasonably healed, for at least 7 days after the urgent surgical procedure.

5.2.5 Patient Compliance and Replacement

To the extent possible, patients must strictly follow the standard dosing schedule. Patients who miss 2 of the doses of selinexor or 1/4 of the doses of ibrutinib within the first cycle of treatment in the absence of study drug related toxicity will be discontinued unless these are consecutively missed doses due to a required medical procedure that is unrelated to study drug or an anticipated personal emergency, in which case they should restart the cycle.

Compliance to study medication will be ascertained by use of patient diaries for the days where patient administers the study drug themselves at home and for the drug administration days in the clinic, compliance to study medication will be done by the investigator or delegate and recorded in source documents. The date, time and number of capsules or tablets consumed will be recorded as per study drug schedule. The principal investigator or the designee will account for the number of capsules or tablets dispensed against those returned by the patient. Any deviations and missed doses will be recorded in the case report form and drug accountability logs for verification with the reasons. The investigator / designee will try to ensure complete compliance

with the dosing schedule by providing timely instructions to the patients. Patients withdrawn in cycle 1 because of non-compliance not related to study drug related toxicity will be replaced.

5.3 Definition of Dose Limiting Toxicity

CTCAE version 4.0 is used to grade all adverse events and to provide management guidelines for administrative toxicity. A copy of the CTCAE version 4.0 can be downloaded from the CTEP web site http://ctep.cancer.gov/protocolDevelopment/electronic_applications/ctc.htm.

Definition of DLT for patients receiving selinexor and ibrutinib*	
General	

 Treatment delays >28 days for any toxicity Any grade 5 toxicity 	
Non-hematologic	

 Grade 3 nausea/vomiting or diarrhea lasting for ≥ 7 days while taking optimal supportive medications# Grade 3 anorexia or fatigue lasting for ≥ 7 days while taking optimal supportive care# and with correction of dehydration, anemia, endocrine, or electrolyte abnormalities Grade ≥ 3 AST or ALT elevation lasting for ≥ 7 days OR any Grade ≥ 3 AST or ALT elevation in the setting of bilirubin elevation $> 2 \times$ ULN Any other Grade 3 non-hematological toxicity except alopecia, rash that resolves to Grade 1 in ≤ 7 days, or electrolytes abnormalities correctable with supportive therapy# Any Grade 4 non-hematologic toxicity not specifically listed above 	
Hematologic	

 Grade 4 neutropenia [absolute neutrophil count (ANC) $< 500/\text{mm}^3$] (for patients with baseline ANC $\geq 1000/\text{mm}^3$) or $\geq 75\%$ reduction of neutrophils (for patients with baseline ANC $< 1000/\text{mm}^3$) lasting ≥ 7 days; Grade 4 thrombocytopenia [platelet count $< 25,000/\text{mm}^3$] (for patients with baseline platelets $\geq 100,000/\text{mm}^3$) $\geq 75\%$ reduction of platelets (for patients with baseline platelets $< 100,000/\text{mm}^3$) that persists for ≥ 7 days; Grade ≥ 3 thrombocytopenia-associated bleeding; or Grade 4 febrile neutropenia (ANC $< 1000/\text{mm}^3$ with a single temperature $\geq 38.3^\circ\text{C}$ or sustained temperature of $> 38^\circ\text{C}$ for over 1 hour). 	
*Assessed during Cycle 1 by CTCAEv4 criteria #Section 4.4 provides detailed supportive care ^For patients with Gilbert's syndrome: $> 2 \times$ baseline	

AEs meeting the above definitions but that are clearly unrelated to study drugs will not be considered DLTs.

Patients will be considered eligible for DLT assessment if they receive at least 2 of 3 planned doses of selinexor and 19 of 21 planned doses of ibrutinib.

In rare instances, an event may fall within the definition of a DLT as defined above, but the event may not be considered a DLT (ie: not clinically meaningful/significant). If this occurs, a meeting

with all investigators, PI and Sponsor will take place to thoroughly review the event and supporting data and the reasons for not considering the event a DLT will be clearly documented with supporting rationale. Conversely, other events may occur which do not meet the definition of a DLT but are concerning to the investigators and sponsor and may be then considered to be DLTs. We will also consult the DSMC team for input.

Management and dose modifications associated with the above adverse events are outlined in Section 5.

Dose escalation will proceed within each cohort according to the following scheme. Dose-limiting toxicity (DLT) is defined above.

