6. DOSING DELAYS/DOSE MODIFICATIONS

Toxicities that occur in cycle 1 that are DLTs (Section 4.2) will result in protocol removal. Adverse events that are not defined as DLTs and / or occur in cycles 2 and higher will lead to dose delays and modifications as detailed below. No dose reduction below ibrutinib 140 mg and selinexor 20 mg/week will be allowed. If a patient experiences several adverse events, and there are conflicting recommendations, the investigator should use the recommended dose adjustment that reduces the dose to the lowest level. Missed doses will not be replaced. Treatment delays for adverse events exceeding 28 days will lead to protocol removal unless approved by the principal investigator.

Ibrutinib-related lymphocytosis, for the purposes of this protocol, is defined as an elevation in blood lymphocyte count of $\geq 50\%$ compared with baseline count in conjunction with unequivocal improvement in at least 1 other disease-related parameter including lymph node size, spleen size,

hematologic parameters (hemoglobin or platelets), or disease-related symptoms. Ibrutinib-associated treatment-related lymphocytosis generally occurs within the first few weeks of therapy, peaks within the first few months, and resolves slowly. Patients with isolated lymphocytosis in the setting of reduced disease burden or improvement in hemoglobin/platelets should not be considered to have progressive disease.

Asymptomatic treatment-related lymphocytosis should not be considered an adverse event. Subjects with treatment-related lymphocytosis in the absence of other disease-related symptoms should be encouraged to remain on study treatment and continue with all study-related procedures.

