11.1.1 Definitions

Evaluable for toxicity. All patients will be evaluable for toxicity from the time of their first treatment with selinexor.

Evaluable for response. Only those patients who have received at least four weeks of therapy and have had their disease re-evaluated will be considered evaluable for response. These patients will have their response classified according to the definitions stated below. (Note: Patients who exhibit objective disease progression prior to the end of 4 weeks will also be considered evaluable.)

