13.3 Evaluability

Any patient who is eligible for the trial and has received at least one dose each of the selinexor and ibrutinib will be evaluated for toxicity (descriptive summary as well as dose escalation determination in the first two cohorts) and for response. Patients who are not evaluable for toxicity at a given dose level will be replaced.

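### Sections 5.3 and 13.3 give conflicting rules for who counts in the DLT assessment, and each can lower the DLT rate

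*Combined protocol and SAP*

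**What the plan says.** The rules that bear on who counts are these:

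- **Section 5.3** makes patients "eligible for DLT assessment if they receive at least 2 of 3 planned doses of selinexor and 19 of 21 planned doses of ibrutinib". It adds no exception for a patient who has a DLT.
- **Section 13.3** says that an eligible patient who "has received at least one dose each of the selinexor and ibrutinib will be evaluated for toxicity", and gives the purpose as "descriptive summary as well as dose escalation determination in the first two cohorts". It then says: "Patients who are not evaluable for toxicity at a given dose level will be replaced".
- **Section 11.1.1** is broader: "All patients will be evaluable for toxicity from the time of their first treatment with selinexor". It does not mention DLT.
- **Section 5.2.5** has a second replacement rule, limited to patients withdrawn in cycle 1 for non-compliance that is not due to drug toxicity.
- **Section 6** says what follows the event: "Toxicities that occur in cycle 1 that are DLTs (Section 4.2) will result in protocol removal".

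Section 13.4 names DLT as the primary endpoint. Like Section 6, it points to a Section 4.2 that the current numbering does not contain; the definition is in 5.3. No section says whether 5.3 or 13.3 sets the denominator.

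**The concern.** An exposure minimum is reasonable for a patient without a DLT, who must have had enough drug and enough observation to count as a non-event. It is not reasonable for a patient with a DLT, whose low exposure may be the result of the event. Applied without an exception, 5.3 excludes patients because of the outcome being estimated.

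Falling back on 13.3 does not solve this. It requires a dose of both drugs, although most new starters receive selinexor alone in the first week. It also sets no minimum observation for a patient without a DLT.

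The DLT data drive the modified CRM, the MTD (defined through a DLT probability below 0.30), the stopping rule (10-12 patients at a dose level that the model suggests again, or 36 evaluable patients) and the reported DLT probability with its 95% interval (Sections 13.1 and 13.7). All the errors described here point towards making a dose look safer than it is.

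**Working it through.** **1. The plan's own counts.** Section 5.2 gives ibrutinib on Days 8-28 of cycle 1: 28 - 8 + 1 = 21 doses. Selinexor on Days 1, 8 and 15 is 3 doses. Both denominators in 5.3 are reproduced for a patient on weekly selinexor who starts ibrutinib on Day 8.

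**2. When 5.3 can first be met.** The second selinexor dose falls on Day 8, so ibrutinib is the binding condition.
- Start on Day 8: the 19th dose falls on Day 8 + 19 - 1 = 26.
- Already on ibrutinib (Days 1-28 under 5.2): the 19th dose falls on Day 19.

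A patient taken off protocol for a DLT before that day fails 5.3.

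**3. Holds without removal.** Only 21 - 19 = 2 doses may be missed. Sections 6.1 and 6.2 hold ibrutinib for Grade 3 or higher cytopenia (with an exception for some patients with low baseline counts), for at least 7 days after Grade 3 or higher bleeding, and for Grade 3 diarrhea. They do not hold it for Grade 3 nausea, vomiting or fatigue, so those events cost fewer doses.

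**4. Share of DLTs that would fail 5.3.** The documents give no onset times. The table assumes onset uniform over Days 1-28.

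| Ibrutinib in cycle 1 | Stops at onset | Continues 7 days from onset |
|---|---|---|
| Starts Day 8 | Days 1-26: 26/28 = 93% | Days 1-19: 19/28 = 68% |
| Already on it | Days 1-19: 19/28 = 68% | Days 1-12: 12/28 = 43% |

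The 93% becomes 25/28 = 89% if the dose on the onset day is taken. With a Day 8 start and 7 more days of dosing, the share is 5/14 = 36% if onset is confined to Days 15-28, and 0% if confined to Days 22-28. The range is therefore 0% to 93%.

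**5. Effect on the rate.** If a fraction f of DLT patients is dropped and replaced, a true rate p is observed as p(1 - f)/(1 - pf).
- p = 0.30, f = 0.25: 0.225/0.925 = 0.243.
- p = 0.30, f = 0.50: 0.150/0.850 = 0.176.
- p = 0.40, f = 0.50: 0.200/0.800 = 0.250.

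As a rough guide to the decision, the binomial chance of at most 3 DLTs in 12 patients at a true rate of 0.40 is 0.225 with no exclusion, 0.393 at f = 0.25 and 0.649 at f = 0.50. The MCRM decides through a fitted model, so these are not its operating characteristics.

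**6. The gaps in 13.3.** A patient due to start ibrutinib on Day 8 and removed for a DLT on Days 1-7 has had no ibrutinib. That patient fails 13.3 and, by its next sentence, is replaced. In contrast, a patient who leaves on Day 9 for progression after one dose of each drug enters the escalation decision as DLT-free.

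**7. Denominators and window.**
- Twice-weekly selinexor (Section 5.2.3) reaches 2 x 2 = 4 doses in two weeks, so 3 planned doses does not describe it. The same section lists Days 1, 8 and 15 for all doses; these statements must be reconciled.
- For a patient on ibrutinib from Day 1, 19 doses is 19/28 = 68% of plan, against 19/21 = 90% for a new starter.
- Section 5.2.5 discontinues at one quarter of ibrutinib doses missed without drug toxicity (21/4 = 5.25). A new starter who misses 3-5 doses stays on study but fails 5.3.
- DLT is assessed in cycle 1, but one criterion is "Treatment delays >28 days for any toxicity", which cannot be completed inside a 28-day cycle. A criterion of at least 7 days cannot be completed by Day 28 if onset is on Day 23 or later (28 - 23 + 1 = 6 days).

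**The case against.** The best defence is that 13.3 is in the statistical section and expressly covers dose escalation, so it governs. Under it, a DLT patient with one dose of each drug counts. Section 7.14 has the team review all toxicities at a dose level to inform the model, and 5.3 lets the investigators and sponsor class further events as DLTs. Section 11.1.1 is a general safety statement, not a competing DLT rule. The window in which 13.3 loses a DLT is narrow, because many criteria need at least 7 days' duration. Finally, only two dose levels remain, and the August 2016 return to level 1 rested on events that were not formally DLTs (Section 5.1), so that decision did not turn on this count.

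Much of this stands. Section 11.1.1 needs only a cross-reference, and nothing shows that a DLT patient was actually excluded. But the documents do not give 13.3 precedence: 5.3 is the section that defines the endpoint and says who is eligible for its assessment. The discretion in 5.3 reclassifies events, not patients. Narrow or not, the Days 1-7 gap and the missing minimum for DLT-free patients are in 13.3 itself. Section 13.7 still requires a DLT probability and interval at the selected dose, and Cohort 3 uses 40 mg weekly.

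**Conclusion.** The conflict is plain on the text, and neither rule is sound as written. Under 5.3, DLT patients can be excluded because of their DLT. Under 13.3, a DLT before ibrutinib starts is excluded and replaced, and minimal exposure without a DLT counts as DLT-free. Each can only lower the DLT rate. The two sets of harms belong to different rules and should not be added together.

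The size cannot be fixed from the documents. The figures of 24% and 18% for a true 30% rest on assumed fractions (25% and 50%) and on the dropped patients being replaced.

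A reader might infer more than the text supports:
- **That most DLT patients fail 5.3.** This depends on onset timing and continued dosing; the computed range is 0% to 93%.
- **That every DLT before Day 26 fails.** This is untrue for patients already on ibrutinib, or where dosing continues while a duration criterion is being met.
- **That DLT patients who fail 5.3 are replaced.** Replacement is explicit only for those who never received one of the drugs; otherwise 5.2.5 confines it to non-toxicity reasons.
- **That a delay of more than 28 days is incompatible with 19 of 21 doses.** It is not: a patient can complete cycle 1 and then have cycle 2 delayed.
- **That the primary DLT rate is biased.** This is a risk from unreconciled rules, not a demonstrated property of the analysis.

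The matter still needs correcting, because it sets the denominator of the primary endpoint.

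**What to change.** Put one DLT-evaluable definition in 5.3 and 13.3, and cross-refer to it from 5.2.5 and 11.1.1:

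1. Every treated patient with a DLT arising in cycle 1 counts, whatever the exposure.
2. A patient without a DLT counts if observed through cycle 1 and if a stated minimum share of that patient's own planned doses was taken. This also removes the fixed denominators of 3 and 21.
3. Only DLT-free, under-exposed patients are replaced.
4. Onset in cycle 1 decides membership. Such events are followed past Day 28 to judge the duration and delay criteria.
5. Patients already treated are re-classified under this definition before the DLT probability and its 95% interval are reported.

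Correct the pointers to Section 4.2 at the same time.

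The cost is wording in four sections and a small re-classification. The downside for the sponsor is that the reported DLT rate may be higher.

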5.4 Concomitant Medications

Concomitant medication is defined as any prescription or over-the-counter preparation, including vitamins and supplements. All of a patient's concomitant medications must be recorded on the case report form from 14 days before Day 1 through the end of the patient's study participation.

